5.3 Exclusion criteria

1. History of transformation to aggressive disease histology (Large cell lymphoma) within 2 years prior to enrollment.
2. Malignant disease, other than that being treated in this study. Exceptions to this exclusion include the following: malignancies that were treated curatively and have not recurred within 2 years prior to study entry; completely resected basal cell and squamous cell skin cancers, superficial bladder cancer, and completely resected carcinoma in situ of any type.
- 3a. Received cytotoxic or small molecule targeted anti-neoplastics, any experimental therapy in combination with ibrutinib as first line therapy or as a sequential combination partner, within 14-days or 5 half-lives whichever is shorter before the first dose of study treatment. For subjects that received antibodies or immunotherapies, the washout period is 4 weeks prior to study treatment. Patient must have recovered from any adverse effects of prior treatment prior to enrollment.

Protocol amendment 06 exclusion criterion #3a (denotes the first change to criterion #3)

4. Non-palliative radiotherapy within 2 weeks prior to the first dose of study drug. Palliative radiotherapy to a limited field, such as for the treatment of bone pain or focally painful tumor mass is allowed. To allow for assessment of response to treatment, patients must have remained measurable disease that has not been irradiated
5. History of hypersensitivity to any of the study drugs or to drugs of similar chemical classes (e.g., mAb of IgG1 class)
6. Receipt of live vaccine within a two month period before VAY736 treatment. As of Amendment 6, patients who received live vaccine within 4 weeks before VAY736 will be excluded.
7. All acute toxic effects of any prior antitumor therapy (including ibrutinib) resolved to \leq Grade 1 before study enrollment (with the exception of alopecia, grade 2 neurotoxicity, or grade 2 or 3 bone marrow parameters)
8. Presence of active CNS disease
9. Known history of HIV infection
10. [REDACTED]

11. Active, uncontrolled autoimmune cytopenias (including autoimmune hemolytic anemia or immune thrombocytopenia)
12. Current treatment with medications or consuming foods that are strong/moderate inhibitors or strong inducers of CYP3A that cannot be discontinued at least one week

prior to the start of treatment. Refer to [Section 6.4.3](#) for guidance on prohibited medication.

13. Risk factors for Torsades de Pointes (TdP) including uncorrected hypokalemia or hypomagnesemia, history of cardiac failure, or history of clinically significant/symptomatic bradycardia
14. Impaired cardiac function or clinically significant cardiac disease, including any of the following:
 - Clinically significant and/or uncontrolled heart disease such as congestive heart failure requiring treatment (NYHA Grade ≥ 2), uncontrolled hypertension or clinically significant arrhythmia
 - Acute myocardial infarction or unstable angina pectoris < 3 months prior to study entry
15. Patients with impaired hepatic function as defined by Childs-Pugh class B or C.
16. History of stroke or intracranial hemorrhage within 6 months prior to start of study drug
17. Evidence of active ongoing systemic bacterial, mycobacterial, fungal, or viral infection at the time of study enrollment. Note: Subjects with localized fungal infections of skin or nails are eligible. Subjects may be receiving prophylactic antiviral or antibacterial therapies at the discretion of the investigator.
18. Impairment of gastrointestinal function or gastrointestinal disease that may significantly alter the absorption of study drugs, with the exception of prior gastrectomy (e.g., ulcerative disease, uncontrolled nausea, vomiting, diarrhea, malabsorption syndrome)
19. Unable or unwilling to swallow the oral drug as per dosing schedule
20. Two weeks since major surgery treatment (mediastinoscopy, insertion of a central venous access device and insertion of a feeding tube are not considered major surgery)
21. Current use of therapeutic doses of warfarin sodium or any other Coumadin-derivative anticoagulants.
22. Ongoing immunosuppressive therapy, including systemic corticosteroids for treatment of CLL. Note: Subjects may use topical or inhaled corticosteroids as therapy for comorbid conditions and low-dose systemic corticosteroids (≤ 25 mg/day of prednisone or equivalent) for endocrine or rheumatologic conditions. During study participation, subjects may receive systemic or other corticosteroids as pretreatment for VAY736 infusions or as needed for treatment-emergent comorbid conditions.
23. Life-threatening illness, medical condition or organ system dysfunction which, in the investigator's opinion, could compromise the subject's safety, or put the study outcomes at undue risk

24a. [REDACTED]

[REDACTED]

[REDACTED]

[REDACTED]

[REDACTED]

Protocol amendment 06 exclusion criterion #24a (denotes the first change to criterion #24)

6 Treatment

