1.2.4.1.2 Clinical trial data with ibrutinib in CLL

The safety and efficacy of ibrutinib in patients with CLL/SLL were demonstrated in one uncontrolled trial and three randomized, controlled trials. The most commonly occurring adverse reactions ($\geq 20\%$) in patients with CLL/SLL receiving ibrutinib were neutropenia, thrombocytopenia, anemia, diarrhea, musculoskeletal pain, nausea, rash, bruising, fatigue, pyrexia and hemorrhage. Four to 10 percent of patients receiving ibrutinib in patients with CLL/SLL discontinued treatment due to adverse reactions. These included pneumonia, hemorrhage, atrial fibrillation, rash and neutropenia (1% each). Adverse reactions leading to dose reduction occurred in approximately 6% of patients. In an open-label, multi-center trial conducted in 48 previously treated CLL patients, the ORR was 58.3% (95% CI: 43.2%, 72.4%), all partial responses. None of the patients achieved a complete response. The DOR ranged from 5.6 to 24.2+ months. The median duration of response (DOR) was not reached ([de Claro et al 2015](#)).

PCYC-1102/1103

The phase 1b/2 PCYC-1102 study included 85 patients with relapsed or refractory CLL or SLL and 31 symptomatic treatment naïve patients with CLL or SLL aged ≥ 65 years. Patients who completed a minimum of 6 treatment cycles with no evidence of disease progression could enroll in a long-term extension study (PCYC-1103) to continue ibrutinib therapy. Treatment consisted of 420 or 840 mg/day ibrutinib administered orally until progressive disease or poor tolerance ([Byrd et al 2013](#), [Byrd et al 2015](#)).

After a median follow-up of 22.1 months, 22 (71%) of the 31 symptomatic treatment naïve patients achieved an objective response (95% CI 52.0–85.8); four patients (13%) had a complete response, one patient (3%) had a nodular partial response, and 17 (55%) patients had a partial response ([O'Brien et al 2014](#)). When these data were updated at median 30 months of follow-up, ORR had improved to 84%, with 23% attaining CR, 55% PR, and 6% PR with lymphocytosis (PR-L). The estimated PFS rates was 96% (95% CI, 76.5-99.5%) at 30 months ([Byrd et al, 2015](#)). Five-year follow-up data were recently presented ([O'Brien et al 2016](#)). 65% of patients remained on active treatment, and 92% were progression free. Notably, with continued treatment, the CR rate had further improved to 29%.

PCYC-1115

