1.3.4 Expected overlapping toxicities

Combination toxicology studies have not been conducted. Preclinical and preliminary clinical data available from ongoing studies with VAY736 and ibrutinib monotherapy do not indicate a risk for overlapping toxicities. The most common adverse reactions ($\geq 20\%$) in patients with B-cell malignancies (MCL, CLL/SLL, WM and MZL) treated with ibrutinib were neutropenia, thrombocytopenia, diarrhea, anemia, musculoskeletal pain, rash, nausea, bruising, fatigue, hemorrhage, and pyrexia (see ibrutinib package insert). The most common adverse events attributable to VAY736 were lymphopenia, upper respiratory tract infections and infusion related reactions.

An increased number of infusion reactions occurred in the VAY736-treated patients compared to placebo treated patients despite pre-treatment with paracetamol. All infusion-related reactions were mild to moderate in severity. Symptoms all resolved within 24 hours, either spontaneously or with additional paracetamol treatment (for more information please refer to [VAY736 Investigators Brochure]).

No evidence of VAY736-driven reduction in neutrophil counts or hemoglobin levels have been seen to date in ongoing studies. Significant, but transient and reversible, reductions in lymphocyte and NK cell counts were observed in patients treated with VAY736. These reductions are consistent with the intended PD of the compound and activation and redistribution of these cell types in the process of killing of B cells by ADCC. The transient lowering in these cell counts were resolved in all affected patients by the next scheduled evaluation at study day 7.

2 Rationale

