9. Platelets $\geq 25 \times 10^9/L$ without transfusion support within 7 days of the first dose of study drug. Patients with transfusion dependent thrombocytopenia are excluded.
10. Hemoglobin (Hgb) ≥ 8 g/dL without transfusion support within 7 days prior to the first dose of VAY736.
11. Creatinine Clearance ≥ 30 mL/min using Cockcroft-Gault formula (or similar institutional standard) or creatinine $< 2 \times$ ULN
12. Total bilirubin $\leq 1.5 \times$ ULN (For patients with Gilbert's Syndrome: total bilirubin $< 3.0 \times$ ULN with direct bilirubin $< 1.5 \times$ ULN)
13. Aspartate transaminase (AST) $\leq 3.0 \times$ ULN
14. Alanine transaminase (ALT) $\leq 3.0 \times$ ULN
15. Eastern Cooperative Oncology Group (ECOG) performance status 0-2.
16. Written informed consent must be obtained prior to any screening procedures.
17. Patients with relapsed disease after prior allogeneic stem cell transplant (myeloablative or nonmyeloablative) will be eligible if they meet all other inclusion criteria and:
 - a. Do not have active (chronic or acute) GVHD and no immunosuppression
 - b. Are more than 6 months from transplant

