6.4 Concomitant medications

6.4.1 Permitted concomitant therapy

The patient must be told to notify the investigational site about any new medications he/she takes after the start of the study drug. All medications (other than study drug) and significant non-drug therapies (including physical therapy, herbal/natural medications and blood transfusions) administered during the study must be listed on the Concomitant Medications or the Procedures and Significant Non-Drug Therapies CRF.

The use of growth-factor support (e.g. filgrastim, pegfilgrastim, erythropoietin, or darbepoetin) should follow standard practice according to product information and per institutional guidelines. Growth factors should not be administered to allow for patient eligibility at screening. Blood/platelet transfusions, the use of bisphosphonates and topical steroid products, and daily corticosteroid use of ≤ 10 mg/day prednisone (or equivalent) is permitted at the discretion of the treating physician. Therapeutic doses of anticoagulant will not be permitted. Low doses of warfarin for line patency are allowable.

Limited-field palliative radiotherapy to non-target lesion(s) may be allowed as concomitant therapy following a documented discussion with Novartis. Such local therapies administrated during the study treatment must be listed on the Concomitant radiotherapy/surgery case report form (CRF) page.

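### Exclusion 21 bars only therapeutic coumarins, while Section 6.4.1 bars therapeutic anticoagulation of any class on study, so a patient on a therapeutic non-coumarin agent can be enrolled with no entry-stage rule or stop time

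*Protocol*

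**What the plan says.** Two places in the protocol govern anticoagulants.

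- **At entry.** Section 5.3, exclusion 21: "Current use of therapeutic doses of warfarin sodium or any other Coumadin-derivative anticoagulants". The rule covers one pharmacological class.
- **On study.** Section 6.4.1: "Therapeutic doses of anticoagulant will not be permitted", followed by "Low doses of warfarin for line patency are allowable". The ban is on therapeutic doses and carries no class limit. Prophylactic doses are not barred.

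Three other provisions bear on the point. Exclusion 23 lets the investigator decline a patient with a "Life-threatening illness, medical condition or organ system dysfunction" judged to endanger the patient or the study. Exclusion 12 handles CYP3A drugs, which are also prohibited on study: it excludes patients on inhibitors or "strong inducers of CYP3A that cannot be discontinued at least one week" before treatment starts, and it refers to Section 6.4.3. Appendix 3 opens with a general permission for medication the patient needs unless it is prohibited there, and its Table 14-11 lists CYP3A agents only.

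**The concern.** An entry rule and an on-study rule for the same kind of drug should agree, or the protocol should say how to move a patient from one to the other. Here the entry rule is narrower. A patient on a therapeutic non-coumarin agent satisfies the visible criteria and would breach Section 6.4.1 by continuing the drug. The site learns from 6.4.1 that the drug cannot go on. It does not learn whether the patient should have been declined, or how long before the first dose the drug must stop. Withdrawing anticoagulation from a patient treated for thrombosis is itself a safety decision.

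The stake is bleeding on one side and thrombosis on the other. Section 1.3.4 lists hemorrhage among the most common ibrutinib reactions ("rash, nausea, bruising, fatigue, hemorrhage, and pyrexia"). Section 1.2.4.1.2 names reasons for stopping ibrutinib: "These included pneumonia, hemorrhage, atrial fibrillation, rash and neutropenia (1% each"). Inclusion 9 admits platelets down to 25 x 10^9/L "without transfusion support within 7 days of the first dose of study drug", which is the lower bound of CTC grade 3 in SAP Section 5.3.

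**Working it through.** The check is mainly a comparison of text; the plan states no figure on this point.

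1. **Class covered.** Exclusion 21 covers coumarins. Section 6.4.1 covers anticoagulants without restriction. The difference between them is every therapeutic non-coumarin agent.
2. **Another entry criterion that closes the gap.** None of the readable ones does. Exclusion 14 removes clinically significant arrhythmia and exclusion 16 removes stroke or intracranial hemorrhage within 6 months, so some indications for anticoagulation are already out. No visible criterion addresses a patient anticoagulated for venous thrombosis. Inclusion 3 and exclusions 10 and 24a are redacted.
3. **A washout or stop time elsewhere.** Sections 6.4.2 and 6.4.4 are marked not applicable. Section 6.4.3 and Table 14-11 concern CYP3A interactions. The discontinuation list in Section 7.1.3 does not mention anticoagulants. The SAP mentions anticoagulation only in a laboratory-grading footnote.
4. **Whether the protocol links the two kinds of rule elsewhere.** It does. Exclusion 12 ties entry to the ability to stop the drug, gives a one-week interval and points to the on-study section. Exclusion 21 has none of these.

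**Scale, under an assumption.** Let p be the share of otherwise eligible patients on a therapeutic non-coumarin agent. The documents do not give p; 2.5% to 10% is chosen for illustration only. With n = 20 per expansion arm (Protocol Section 4.1):

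- Chance that an arm contains at least one such patient = 1 - (1 - p)^20.
  - p = 2.5%: 1 - 0.975^20 = 0.397
  - p = 5%: 1 - 0.95^20 = 0.642
  - p = 10%: 1 - 0.90^20 = 0.878
- Extra patients to screen if all of them are excluded = 20/(1 - p) - 20.
  - p = 2.5%: 20/0.975 - 20 = 0.5
  - p = 5%: 20/0.95 - 20 = 1.1
  - p = 10%: 20/0.90 - 20 = 2.2

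The three probabilities equal the N = 20 column of SAP Table 3-1 because the binomial formula is the same. That table concerns adverse-event rates and lends no support to these values of p. Refusals under exclusion 23 would lower the probabilities.

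**The case against.** The best reply is that Section 6.4.1 may be a loosely worded coumarin rule. The sentence after the ban is about warfarin, exclusion 21 is limited to coumarins, and Appendix 3 permits necessary medication that it does not list. On that reading, non-coumarin users were admitted on purpose and the only fault is a missing qualifier in 6.4.1. This stands to the extent that the text does not settle the sponsor's intent. It does not remove the conflict: 6.4.1 as written has no class limit, and the Appendix 3 permission, read literally, adds a second inconsistency. Under either intent, one sentence has to change.

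A second reply is that exclusion 23 already protects such a patient. It allows refusal case by case, but it rests on the investigator's opinion of an illness or dysfunction, does not mention anticoagulants, and leaves the two rules in disagreement.

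A reader might go further and infer that the protocol leaves open whether the drug may be continued, or that each site is free to continue it. The documents do not support this. Section 6.4.1 answers the question of continuing: therapeutic doses are not allowed. Section 12 states that deviations cannot be authorised and that a desired change must become an amendment. The urgent-safety clause in Section 12.1 concerns immediate action for patients already in the study and is not a route for starting a patient on a barred drug.

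**Conclusion.** The mismatch is real and minor. What is missing is an entry criterion that matches the on-study ban or, failing that, a stop time before the first dose. The conclusion rests on the readable criteria and on taking 6.4.1 at its word.

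No count of affected patients can be claimed; the probabilities above show only that such a patient could plausibly appear in a 20-patient arm if use were in the assumed range. Two further inferences should not be drawn. The point is not evidence of added bleeding risk from VAY736: patients must already be taking and tolerating ibrutinib at enrolment (Section 5.1), so part of the bleeding risk precedes the study. Nor is the silence of Section 6.4.3 and Table 14-11 on anticoagulants a fault in itself, since both deal with CYP3A interactions.

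**What to change.** Reword exclusion 21 along these lines: *Therapeutic-dose use of any anticoagulant at present (low-dose warfarin to keep a line patent is acceptable; see Section 6.4.1).* This keeps the existing flat bar on coumarins and extends it to all classes.

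If the sponsor wishes to admit patients who can stop a non-coumarin agent, add a specific interval before the first dose, set by the sponsor, as exclusion 12 does for CYP3A drugs. A phrase such as *before first dose* would not be enough, because it sets no interval. If the sponsor meant to allow non-coumarin agents throughout, leave exclusion 21 alone and limit the 6.4.1 sentence to coumarins.

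The cost is one reworded sentence with a cross-reference and, if the exclusion is widened, a few more screen failures: about 0.5 to 2.2 per 20-patient arm under the assumed range. Arm B is already closed, and SAP Section 1 records that early termination was endorsed on 22-Sep-2023, so the change is useful only for any further enrolment or for reuse of the text in another protocol.

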6.1 Study treatment

The investigational drug VAY736 will be used in combination with the marketed drug ibrutinib.

6.1.1 Dosing regimen

The dosing cycle is 28 days. Patients will receive ibrutinib once daily continuously and VAY736 by i.v. once every 2 weeks (Days 1 and 15). During the dose escalation part of the study, the dose of ibrutinib will be 420 mg. During the dose expansion part of the study, ibrutinib will be continued at the same dose schedule as tolerated before study enrollment, see exclusion criteria in [Section 5.2](#) for additional information on dose level.

A Q4W dosing schedule may also be evaluated if supported by emerging clinical data (e.g., safety or PK/PD or activity). The escalation of the Q4W dosing schedule will be guided by a separate BLRM. The DLT data available from VAY736 Q2W will be used to derive a MAP prior distribution for the Q4W dosing schedule as described in [Section 10.4.2](#). This decision will be formally documented in dose-escalation meeting minutes and distributed to all study sites.

Table 6-1 Dose and treatment schedule

Study treatments	Pharmaceutical form and route of administration	Dose	Frequency and/or Regimen
VAY736	Powder for solution for infusion	As assigned	Once every 2 weeks or every 4 weeks, as assigned
Ibrutinib	Solid dose (tablet or capsule) for oral use	Dose escalation: 420 mg Dose expansion: 420 mg or highest tolerated dose	Daily (28 day cycles)

6.1.1.1 Instructions for ibrutinib administration

- Patients should be instructed to take their dose at approximately the same time on the appropriate days.
- On days when blood for PK samples needs to be collected, the patient should take the dose in the clinic.
- Each dose should be taken with a glass of water and consumed over as short a time as possible unless otherwise instructed.
- Patients should be instructed to swallow capsules/tablets whole and to not chew or open them unless otherwise instructed. Patients may take either tablets or capsules as they are bioequivalent (Please see latest version of the ibrutinib Package Insert)
- Grapefruit, grapefruit juice and Seville oranges should be avoided during the treatment period of the study
- On days of PK/PD sampling, every effort must be made to capture the time of any vomiting within 8 hours of drug administration.
- If vomiting occurs during the course of the treatment, then no re-dosing of the patient is allowed before the next scheduled dose.
- If the patient forgets to take his/her daily dose of ibrutinib, then he/she should take the dose within 8 hours after the missed dose. If more than 8 hours have passed, then that day's dose should be omitted and the patient should continue treatment with the next scheduled dose.
- Refer to the ibrutinib package insert for additional information.

Patients should inform the investigational site staff of any missed or delayed doses.

6.1.1.2 Instructions for VAY736 administration

Refer to VAY736 pharmacy manual for information.

6.1.2 Ancillary treatments

Mild to moderate infusion related reactions have been reported in VAY736 clinical trials of autoimmune diseases. For the first two infusions, premedication for the risk of infusion reactions is required. Premedications should be administered 30 minutes to 2 hours prior to each of the first two infusions of VAY736 and should include oral acetaminophen 1,000 mg (or equivalent), oral or intravenous antihistamine, and intravenous corticosteroid (prednisolone 100 mg or equivalent) or similar prophylaxis based on institutional guidelines. For subsequent infusions

(infusions three and beyond), premedication may be administered if deemed appropriate by the treating physician.

Acute allergic reactions should be treated as needed per institutional standard of care. In the event of anaphylactic/anaphylactoid reactions, this includes any therapy necessary to restore normal cardiopulmonary status. If a patient experiences a Grade ≥ 3 anaphylactic/anaphylactoid reaction, the patient will be discontinued from the study. The CTCAE category of “Infusion related reaction” should be used to describe study treatment related infusion reactions, unless the investigator considers another category, such as “Allergic reaction,” “Anaphylaxis,” or “Cytokine release syndrome” more appropriate in a specific situation.

6.1.3 Rescue medication

Not applicable.

6.1.4 Guidelines for continuation of treatment

Refer to [Section 6.3](#) and [Section 6.3.2](#) and [Table 6-4](#)

